	
 • Supporting caregiver coping • Providing referral for additional support 	
 • Bolster caregiver coping by assessing burden, enhancing their communication with patients, and recommending additional support • Involve other members of the team for patients and caregivers who may be experiencing severe distress (e.g., social work, psychology)
--	--	---

As shown in Table 2 above, the palliative care intervention will focus on the following content areas: 1) addressing patients' physical and psychological symptoms; 2) managing patients' and caregivers' expectations; and 3) providing patients and caregivers with strategies to cope with the illness during HCT. Palliative care clinicians will focus specifically on symptoms we have shown to be prevalent in this population, including nausea, pain and mucositis, fatigue, sleep disturbances, constipation, diarrhea, anxiety and depression.

Ensuring Fidelity of the Palliative Care Intervention: We will take several steps to ensure the fidelity of our study design, training, and intervention delivery as noted in the table below (Table 3). Specifically, for the study design, we will utilize an evidence-based palliative care intervention guide, measure the number and duration of palliative care visits, and monitor the number of participants in the control arm receiving palliative care. Also, we will employ rigorous training procedures with in-person training for site PIs and RAs; and monthly telephone conferences with Drs. [name] and [name] with the site PIs and palliative care clinicians to discuss any issues. To ensure the fidelity of the intervention delivery, we will review palliative care clinicians' documentation to enable us to assess the content of the clinical encounter. Drs. [name] and [name] will independently review electronic surveys completed by the palliative care clinicians to ensure intervention fidelity and conformity between sites in addressing the domains and topics as specified by the guide. Based on this review, Drs. [name], [name], and [name] will provide constructive feedback as needed to individual clinicians to ensure they are delivering the intervention in a consistent fashion. The site PIs will also review palliative care notes in the health record to ensure adherence to the intervention guide content and provide feedback to clinicians at the site research meetings.

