As done in our prior trial,³⁴ patients randomized to the transplant care alone arm will not meet with palliative care clinicians, though they may consult with palliative care at their request or at the discretion of their treating clinicians. In most transplant centers, supportive care measures are instituted at the discretion of the transplant oncology team and include symptom-directed therapies for nausea, pain, and diarrhea. Additionally, social workers are occasionally available to assist in helping patients and families emotionally during the HCT process. We will collect data on social work consultations and consider them as a covariate in our analyses. Patients randomized to transplant care alone will receive all supportive care measures as instituted by the transplant oncology team including social work consultations upon request. We anticipate minimal cross contamination, as the rate of palliative care consultation is less than 5% for patients admitted for HCT at our participating sites. In our prior single center trial, only two patients randomized to transplant care alone received palliative care consultations. Notably, the palliative care intervention did not lead to significant changes in supportive care practices implemented by the transplant clinicians. While patients undergoing HCT often interact post-transplant, they are typically isolated during the acute hospitalization period and have minimal interactions. Patients are also typically seen by multiple providers including nutritionists, physical therapists, residents, nurse practitioners, and social workers. Consequently, patients randomized to transplant care alone will not notice the lack of interaction with palliative care clinicians. Therefore, we do not anticipate that cross-contamination will be a significant issue in the proposed trial.

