10.0 Data and Specimen Banking: Not applicable

10.1 Data analysis

Specific Aim 1: To demonstrate the efficacy of inpatient integrated palliative and transplant care for improving patient-reported outcomes: Analyses will begin with descriptive and graphical summaries of the endpoints and evaluation of whether a normality assumption is reasonable for the endpoint or whether transformation is necessary. All statistical tests will be two-sided with an alpha level of 0.05. For all secondary and exploratory outcomes, we will use the false discovery rate (FDR) control method to address the issue of multiple testing. We selected an FDR of 0.15, which denotes the acceptable percentage of results that potentially represent false positives.⁶² The primary endpoint of the study will be to compare patient QOL (FACT-BMT) scores at week-2 between the study groups controlling for baseline values and demographic and clinical factors (as necessary for any imbalances in baseline variables) using a linear regression model. We will also compare secondary endpoints including patients' symptoms (ESAS), fatigue (FACT-Fatigue), depression and anxiety symptoms (HADS and PHQ9), and coping (Brief Cope) at week-2 between the study groups using linear regression models controlling for baseline values and clinical factors (as necessary for any imbalances in baseline variables). In the event that the effect of the intervention differs by transplant type, conditioning intensity, or other patient characteristics, we will examine these variables as interaction terms in the linear regression analyses. Finally, we will compute the effect size and Reliability Change Index to assess practical and clinical significance in the degree of change in the primary and secondary outcomes.

We will also utilize linear mixed models of the longitudinal data, allowing us to account for dependency among means over time and to control for demographic and clinical factors (as necessary for any imbalances in baseline variables) when examining change between groups in outcomes of interest across multiple time points (i.e., baseline, 2 weeks, 3, 6, and 12 months post-HCT). We will estimate practical and clinical significance of these outcomes (Cohen's d and Reliability Change Index).

Specific Aim 2: To assess the impact of inpatient integrated palliative and transplant care on caregiver-reported QOL and psychological outcomes: We will similarly compare caregivers' QOL

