PROTOCOL TITLE: Multi-Site Randomized Trial of Inpatient Palliative Care for Patients with Hematologic Malignancies Undergoing Hematopoietic Stem Cell Transplantation

(CARGOQOL), depression and anxiety symptoms (caregivers HADS and PHQ9), and coping at week-2 using linear regression models controlling for baseline values and clinical factors (as necessary for any imbalances in baseline variables). We will also use linear mixed models of the longitudinal data, allowing us to account for dependency among means over time and to control for demographic and clinical factors (as necessary for any imbalances in baseline variables) when examining change between groups in outcomes of interest across multiple time points (i.e., baseline, 2 weeks, 3, 6, and 12 months post-HCT). We will again estimate practical and clinical significance of these outcomes (using Cohen's d and Reliability Change Index).

Specific Aim 3: To explore mediators and moderators of the effect of the palliative care intervention on patient-reported QOL: We will conduct bootstrapped tests of mediation to determine whether group differences in patient-reported QOL (FACT-BMT) are mediated by improved symptom burden (mediators: ESAS/HADS), or coping (mediator: Brief Cope). Although in our randomized trial, we did not identify moderators of the effect of the palliative care intervention, we will test for potential moderators to ensure generalizability of our findings, as other studies have found age and gender as moderators of the impact of palliative care in patients with lung cancer.⁶³ We will create interaction terms for the linear regression analyses and linear mixed models to examine whether differences in patient-reported QOL are moderated by patient factors (age, gender, race), transplant factors (type of HCT, conditioning intensity), or study site.

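### Section 9.3 leaves open adjusting for social work consultations, which fall largely after randomisation and which assignment can change; they should be kept out of the efficacy models.

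*Combined protocol and SAP*

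**What the plan says.** Section 9.3 (Transplant Care Alone) carries the sentence at issue: "We will collect data on social work consultations and consider them as a covariate in our analyses". No model, endpoint or time window follows, and nothing limits the data to consultations before randomisation. The same section says that "social workers are occasionally available to assist in helping patients and families emotionally during the HCT process", and that control patients receive all supportive care from the transplant team, "including social work consultations upon request".

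Table 2 in section 9.2, under coping with illness, gives palliative care clinicians this instruction: "Involve other members of the team for patients and caregivers who may be experiencing severe distress (e.g., social work, psychology").

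Section 10.1 sets the covariates. The primary week-2 FACT-BMT comparison is made "controlling for baseline values and demographic and clinical factors (as necessary for any imbalances in baseline variables) using a linear regression model". The week-2 caregiver comparisons use "linear regression models controlling for baseline values and clinical factors (as necessary for any imbalances in baseline variables"). The mixed models follow the same baseline-imbalance rule. Social work appears in none of them, and it is not among the Aim 3 mediators, which are ESAS/HADS and Brief Cope.

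**The concern.** A covariate in a randomised comparison should be fixed before assignment, or at least be beyond its influence. Social work consultation during the transplant stay is neither. The palliative care arm has an extra route to it through Table 2, while controls get it on request or through the transplant team. Distress also prompts it, and distress lies close to the quality-of-life and mood endpoints.

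Entering such a variable can do harm in two ways. If consultation helps patients, adjustment removes the part of the benefit that runs through it. If consultation mainly marks distress, patients with the same consultation status in the two arms are no longer comparable in distress, and the arm estimate shifts even if consultation does nothing. The second shift does not depend on the size of the true effect, so it also appears when there is no effect.

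Because 9.3 says only that the covariate will be considered, the decision could be taken after results by arm are known.

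**Working it through.** **1. The plan's own figure.** Section 10.2 gives N = 360, 10% missing at week 2, a difference of 6.9, SD 20 and two-sided 0.05, with 87% power. Per arm: 360 × 0.90 / 2 = 162. SE = 20 × √(2/162) = 2.22, and 6.9 / 2.22 = 3.105. The noncentral t distribution gives 87.2% (normal approximation 87.4%), so the stated figure is reproduced. It makes no use of social work data.

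**2. Timing.** Section 5.1 orders the steps as consent and baseline questionnaire, registration, then randomisation. Patients are approached from two weeks before admission to 72 hours after it (96 with public holidays). Section 9.3 places social work support within the transplant course. Some consultations may precede randomisation, but most should follow it. This is an inference; the documents give no dates for consultations.

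**3. Can assignment change it?** Yes, through the Table 2 instruction. Section 19.2 adds that transplant social workers at all sites will help participants in distress, which supports the link between distress and consultation.

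**4. What adjustment would do (illustration).** The documents give no consultation rates, no strength of the distress link and no effect of consultation on FACT-BMT. All of these are assumed here:

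- A = arm, U = in-hospital distress, S = consultation (0/1).
- logit P(S = 1) = -0.8 + g·A + k·U, with g = 0.8, 0 or -0.8.
- Y = (6.9 - b·d)·A + b·S + 10·base - 10·U + 14.1·e, where U, base and e are standard normal and d is the arm difference in P(S = 1). The total effect therefore stays at 6.9. SD is about 20 within arm.
- Shift = arm coefficient with S in the model, minus the coefficient without it (both adjusted for base).

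Shifts in FACT-BMT points, from simulations of 2 to 4 million subjects per scenario:

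| Distress link k | Use, control vs intervention | b = 0 | b = 5 | b = 10 |
|---|---|---|---|---|
| 1 | 34% vs 50% | +1.33 | +0.53 | -0.27 |
| 1 | 34% vs 21% | -1.13 | -0.47 | +0.20 |
| 0.5 | 32% vs 50% | +0.86 | about 0 | -0.95 |
| 0 (pure mediator) | 31% vs 50% | 0 | -0.95 | -1.90 |
| any of these | equal use | 0 | 0 | 0 |

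The pure-mediator row can be checked by hand, since the shift is -b·d: -5 × (0.50 - 0.31) = -0.95 and -10 × 0.19 = -1.90. In the first row at b = 0, setting the true effect to zero leaves the shift at about +1.3.

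**5. Scale.** In the first row at b = 0 the baseline-adjusted residual SD is 17.28, so SE = 17.28 × √(2/162) = 1.92. The +1.33 shift is 1.33 / 1.92 = 0.69 of a standard error.

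**6. Sensitivity to the assumed model.** A threshold (probit-type) model for consultation, with use rising from 36% to 50%-64% and a distress-QOL correlation of 0.3 to 0.7, gave upward shifts of 0.9 to 4.4 points. A mediator calculation with arm gaps of 10 to 30 percentage points and a consultation benefit of 3 to 8 points removed 0.3 (0.10 × 3) to 2.4 points (0.30 × 8). The table therefore sets no limit on the shift.

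**The case against.** The strongest reply is that no error is planned. Section 9.3 promises only to consider the covariate, in a paragraph describing the control arm. Section 10.1 is the analysis section, and read literally its baseline rule already excludes a post-randomisation consultation. That much stands: a reader might infer that the primary analysis will be adjusted for social work, and the documents do not say so. The primary model is exposed only if 9.3 is acted on. But 10.1 does not override 9.3 either, and the reference in 9.3 to the trial's analyses is unrestricted. It might have been meant for descriptive or exploratory work, but it does not say that.

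The second reply is that bias also needs use to differ by arm, which nothing shows. Section 9.3 says that "Patients are also typically seen by multiple providers including nutritionists, physical therapists, residents, nurse practitioners, and social workers", and that in the prior trial "the palliative care intervention did not lead to significant changes in supportive care practices implemented by the transplant clinicians". Table 2 names social work only as an example, for severe distress. These points favour a small difference and should temper any claim of material harm. They do not exclude a difference: the prior-trial remark covers what transplant clinicians did, whereas Table 2 concerns what palliative care clinicians do.

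**Conclusion.** The concern holds as a conflict between sections 9.3 and 10.1 that should be closed before analysis. The wording gap is certain. That most consultations follow randomisation, and that assignment can change them, are well-supported readings of the text. Harm needs two further conditions: the 9.3 sentence is acted on, and use differs by arm. If both hold, the arm coefficient stops estimating the effect of assignment in whichever patient or caregiver model is affected.

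The size and direction of the shift cannot be determined from the documents. The +1.3 points (34% vs 50% use, consultation only a marker of distress) and the -1.0 to -1.9 points (31% vs 50%, pure mediator worth 5 to 10 points) rest on assumed rates and links. A reader might take such figures as a ceiling, or as evidence that the trial's result will be biased; neither inference is supported, and equal use gives no shift. This is a matter the sponsor should correct, not a flaw in the primary model as 10.1 defines it.

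**What to change.** In section 9.3, replace the covariate statement with: *social work consultations will be collected and summarised descriptively by study group*.

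In section 10.1, add: *social work consultations after randomisation will not be covariates in the primary or secondary patient and caregiver efficacy models; any other use will be labelled exploratory*.

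The cost is two sentences. Data collection, sample size, the baseline adjustments already in 10.1 and the stated 87% power (recomputed 87.2%) do not change.

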9.4 Selection of Instruments

We selected instruments based on our prior studies and the conceptual framework of our intervention, which seeks to improve patients' and caregivers' QOL and mood, reduce their symptom burden, and enhance their coping strategies, which will ultimately lead to improvement in their QOL and psychological outcomes post-HCT.

- **Demographics:** Patients and caregivers will complete a demographic questionnaire at baseline detailing their age, sex, race, ethnicity, religion, relationship status (caregivers will specify their relationship with patients), educational level, annual household income, and living situation [appendix A].
- **QOL-Patient:** We will use the Functional Assessment of Cancer Therapy-Bone Marrow Transplant (FACT-BMT) to assess QOL, which has been validated for use in patients undergoing HCT.⁵³ The FACT-BMT consists of four subscales assessing well-being across four domains (physical, functional, emotional, and social), as well as additional questions specific to the transplant population. These self-reported measures possess strong psychometric properties and have been validated for patients with leukemia [appendix B].
- **Symptoms-Patient:** We will administer the revised Edmonton Symptom Assessment Scale (ESAS) to assess various symptoms relevant to this population. The revised Edmonton Symptom Assessment Scale has been well validated and extensively studied in patients with cancer undergoing active chemotherapy treatment [Appendix C]⁵⁴.
- **QOL-Caregiver:** We will use the CareGiver Oncology QOL questionnaire (CarGOQOL) to measure caregiver QOL. The CarGOQOL is a 29-items well-validated instrument to measure QOL in multiple domains.⁵⁵ The CarGOQOL has been previously

PROTOCOL TITLE: Multi-Site Randomized Trial of Inpatient Palliative Care for Patients with Hematologic Malignancies Undergoing Hematopoietic Stem Cell Transplantation

validated for caregivers of patients with cancer including hematologic malignancies [Appendix D]

- **Mood (patient & caregivers):** We will use the Hospital Anxiety and Depression Scale (HADS) to assess symptoms of depression and anxiety in all study participants (patients and caregivers). The HADS is a 14-item questionnaire that contains two 7-item subscales assessing depression and anxiety symptoms during the past week [appendix E]⁵⁶. Used extensively in samples of patients with cancer and their caregivers, the questionnaire consists of a four-point item response form that quantifies the degree to which participants experience mood symptoms. Scores on each subscale range from 0 to 21, with a cutoff of 8 or greater denoting clinically significant anxiety or depression. We will also use the PHQ-9 to assess major depressive syndrome in study participants. The PHQ-9 is a nine-item measure that evaluates symptoms of major depressive disorder according to the criteria of the diagnostic and statistical manual of mental disorders-IV [appendix F]⁵⁷.
- **PTSD symptoms - Patient:** We will use the Post-Traumatic Stress Disorder Checklist (PCL) to assess symptoms of post-traumatic stress in patients. The PCL is a 17 item self-reported measure that evaluates symptoms of post-traumatic stress disorder according to the criteria of the Diagnostic and Statistical Manual of Mental Disorders-IV [Appendix G].³⁹
- **Fatigue – Patient:** we will use the 13-item FACT-Fatigue scale to assess fatigue symptoms [appendix H].⁵⁸
- **Coping strategies (patient and caregiver):** We will use the Brief Cope, a 28-item questionnaire that assess 14 methods of coping (e.g., self-distraction, humor, denial) using a 4-point Likert scale [appendix I].⁵⁹

9.5 *Data from the Electronic Health Record:*

Study staff will collect clinical, disease, and transplant characteristics at baseline including: ECOG Performance Status at the time of HCT, clinical comorbidities as measured by the HCT-Comorbidity Index,⁶⁰ underlying diagnosis, date of diagnosis, disease status at the time of HCT, disease risk based on the Disease Risk Index,⁶¹ conditioning regimen, donor type, donor source, date of HCT, and hospital length-of-stay. We will also collect data on the incidence and severity of acute and chronic graft-versus-host disease and the incidence of relapse at one year post-HCT as these outcomes are associated with QOL.

9.6 *Data on Palliative Care Visits:*

As noted previously, palliative care clinicians will enter data on the nature of their initial visit and weekly visits with study participants, using a Research Electronic Data Capture (REDCap) survey. The REDCap survey assesses domains and topics covered during the palliative care visit. We developed and refined the domains of inpatient palliative care and detailed the possible topics addressed under each domain based on our previous trial. In our single center trial, all palliative care clinicians completed REDCap entries after their clinical interactions with patients for 100% of their encounters. We will use the identical study procedures to ensure documentation of all the palliative care clinical interactions in this proposed trial. Specifically, prior to the study start all participating palliative care clinicians will be trained on the use of the REDCap survey and the importance of entering these data. After the initial visit and on weekly

PROTOCOL TITLE: Multi-Site Randomized Trial of Inpatient Palliative Care for Patients with Hematologic Malignancies Undergoing Hematopoietic Stem Cell Transplantation

basis, the research assistant will send a secure email with the patient's name with a link to the REDCap system. If clinicians do not complete the REDCap entry within 48 hours, they will receive a second email with the site PI included on the email.

Study staff will administer self-report study assessments at baseline, week-2 during the transplant hospitalization (+ 2 day window), at three, six, and twelve months post-HCT (+/- 2 week window). If the patient prefers verbal administration of the assessment, the study staff member will be someone blinded to the intervention assignment. The demographic questionnaire, included in the patient and caregiver baseline assessments only, will ask study participants to provide their email address to allow us to email study assessments to those who do not have a scheduled appointment within the follow-up time points. If patients do not have an email address, we will either send them paper copies of the survey or ask them to complete them verbally over the telephone. We will track the methods of survey completion among participants. The entire study assessment battery will be administered at all time points (except demographics) and takes approximately 20 minutes to complete. The selected self-report measures have strong psychometric properties and have been well validated in previous studies in this population. All study measures are available in both English and Spanish.

